1.1 Title

Rivaroxaban versus Warfarin in Patients with Atrial Fibrillation ([ROCKET AF trial](#))

1.2 Intended aim(s)

To compare the risk of stroke or systemic embolism in nonvalvular atrial fibrillation (AF) patients at increased risk for stroke with rivaroxaban versus warfarin use.

1.3 Primary endpoint for replication

The primary outcome of the study was composite of stroke (ischemic or hemorrhage) and systemic embolism.

1.3.1 Required power for primary endpoint and noninferiority margin (if applicable)

The test was designed for noninferiority. The most conservative approach was chosen, selecting the lower limit, 1.46 to obtain a 95% power with a 1-sided α equal to 0.025. With expected study duration was 40 months, project event rate of 2.3% per 100 patient years in the warfarin group, and 14% annual attrition rate, 405 events were selected as the prespecified target to ensure a robust statistical result.

1.4 Secondary endpoint for replication (assay sensitivity) and RCT finding

Major bleeding; HR = 1.04 (95% CI 0.90-1.20)

1.5 Trial estimate

HR = 0.79 (95% CI 0.66-0.96) comparing rivaroxaban vs warfarin (Patel et al., 2011)

2. Person responsible for implementation of replication in Aetion

[name], [name]., and [name], MPH implemented the study design in the Aetion Evidence Platform. They are not responsible for the validity of the design and analytic choices. All implementation steps are recorded and the implementation history is archived in the platform.

[figure not shown]
3. Data Source(s)

United/Optum, Truven/MarketScan, Medicare

4. Study Design Diagram

The study design diagram visualizes key aspects of the longitudinal study design for expedited review.

Design Diagram – ROCKET AF TRIAL REPLICATION

^aCensoring criteria

- Occurrence of outcome
- Specified Date reached
- Death
- Switch (within comparison grp)
- Start of additional Exposure
- Nursing home admission
- End of index exposure
- Disenrollment

5. Cohort Identification

5.1 Cohort Summary

This study will involve a new user, parallel group, propensity score-matched, retrospective cohort study design comparing rivaroxaban (at a daily dose of 20mg or 15 mg) to warfarin users. The patients will be required to have continuous enrollment during baseline period of 180 days before initiation of rivaroxaban or warfarin (index date). We will restrict the analyses to patients with a diagnosis of atrial fibrillation with risk factors for stroke or systemic embolism.

5.2 Important steps for cohort formation

New users (defined as no use in 180 days prior to index date) of an exposure and a comparator drug will be identified.

5.2.1 Eligible cohort entry dates

Rivaroxaban was approved for non-valvular atrial fibrillation on November 4, 2011.

- For Marketscan: November 4, 2011 -December 31, 2018 (end of data availability).
- For Medicare: November 4, 2011 -December 31, 2017 (end of data availability).
- For Optum: November 4, 2011 -December 31, 2019 (end of data availability).

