Excluded based on Exclusion #3d.1 - Use of aspirin > 100 mg, #3d.2 - Use of fibrinolytic agents, #3d.3 - Use of Aspirin + thienopyridines, #3d.4 - Use of cangrelor, #3f - Use of CYP inhibitors, #3g - Use of CYP inducers	-1,020	45,684	-1,024	53,726	-4,503	148,866
Excluded based on Exclusion #3h – Anemia & #3i - Pregnancy	-1,382	44,302	-1,294	52,432	-6,940	141,926
Excluded based on Exclusion #3k - HIV infection	-13	44,289	-7	52,425	-12	141,914

Excluded based on Exclusion #3l - Severe renal impairment	-3,281	41,008	-2,012	50,413	-7,391	134,523
Excluded based on Exclusion #3m - Liver disease	-192	40,816	-170	50,243	-466	134,057
Excluded based on Exclusion #4a - CCI (180 days)- ICD9 and ICD10 v2	-40	40,776	-31	50,212	-400	133,657
Excluded based on Exclusion #4b - drug addiction or alcohol abuse	-157	40,619	-106	50,106	-231	133,426
Excluded based on Exclusion #4f - Non-compliance	-15	40,604	-21	50,085	-196	133,230
Final cohort		40,604		50,085		133,230

Due to CMS cell suppression policy, all values less than 11 are denoted with **

* Medicare database includes all patients using a novel oral anticoagulant and a subset of patients using warfarin during 2011-2017.

6. Variables

6.1 Exposure-related variables:

Study drug:

The study exposure of interest is initiation of rivaroxaban. Initiation will be defined by no use of rivaroxaban or a comparator in the prior 6 months before treatment initiation (washout period).

Comparator agents-

- Initiators of rivaroxaban will be compared to initiators of-
 - Warfarin

6.2 Covariates:

- Age
- Sex
- Combined Comorbidity Index (CCI), measured over the baseline covariate assessment period, defined as 180 days prior to and including index date

Covariates listed above represent only a small subset of covariates that will ultimately be controlled for in the design and analysis. We use the covariates above only for initial feasibility analyses to judge whether there is likely to be sufficient overlap between treatment groups to proceed with the study. Remaining covariates are defined only after the study has passed the initial feasibility analysis and the initial power assessment and are listed in Table 1 (**Appendix B**).

6.3 Outcome variables and study follow-up:

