After review of initial feasibility and power analyses, complete creation of the remaining covariates (see Table 1 below for list of covariates). Again, using the dummy outcome of a 90-day gap in database enrollment, complete a 1:1 PS-matched analysis. The PS should include the complete list of covariates (excluding laboratory values, which are missing in some patients).

- Provide plot of PS distributions stratified by treatment group.

Note- Please refer to **Appendix B**.

- Report covariate balance after matching.

Note- For Table 1, please refer to **Appendix B**.

- Report reasons for censoring by treatment group.

	Overall	Referent	Exposure
Dummy Outcome	0 (0.00%)	0 (0.00%)	0 (0.00%)
Death	1,879 (1.83%)	946 (1.84%)	933 (1.82%)
Start of an additional exposure	3,238 (3.15%)	1,642 (3.20%)	1,596 (3.11%)
End of index exposure	71,983 (70.13%)	36,022 (70.19%)	35,961 (70.07%)
Specified date reached (Dec 17/Dec 18/Dec 19)	6,822 (6.65%)	3,196 (6.23%)	3,626 (7.07%)
End of patient enrollment	5,237 (5.10%)	2,408 (4.69%)	2,829 (5.51%)
Switch to other NOACs (for censoring) + nursing home admission	13,477 (13.13%)	7,104 (13.84%)	6,373 (12.42%)

- Report follow-up time by treatment group.

Median Follow-Up Time (Days) [IQR]			
Patient Group	Optum	Truven	Medicare
Overall Patient Population	98 [38-209]	98 [44-236]	98 [38-206]
Referent	98 [38-190]	98 [44-192]	98 [38-188]
Exposure	98 [38-231]	119 [44-281]	98 [38-228]

- Report overall risk of the primary outcome.

	Optum	MarketScan	Medicare	Pooled
Risk per 1,000 patients	7.00	7.33	12.05	10.08

10. Final Power Assessment

Date conducted:

- Re-calculate power in the appropriate excel table, using the revised number of matched patients from the PS-match in Section 9. All other parameters in the table should be the same as in Section 8.

- For rivaroxaban vs. warfarin

- Pooled

Superiority Analysis		Non-inferiority Analysis	
Number of patients matched	102,636	Number of patients matched	102,636
Reference	51,318	Reference	51,318
Exposed	51,318	Exposed	51,318
Risk per 1,000 patients	10.08	Risk per 1,000 patients	10.08
Desired HR from RCT	0.79	Assumed HR from RCT	1
Alpha (2-sided)	0.05	Alpha (2-sided)	0.05
		Non-inferiority margin	1.46
Number of events expected	1034.57088	Number of events expected	1034.57088
Power	0.966450516	Power	0.999981559

o Optum

Superiority Analysis		Non-inferiority Analysis	
Number of patients matched	17,900	Number of patients matched	17,900
Reference	8,950	Reference	8,950

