Appendix A

#	ROCKET-AF trial definitions	Implementation in routine care	References/Rationale	Color coding
	Trial details- Primary indication, 4a- Unintended S with label change HR = 0.79 (95% CI 0.66-0.96)		
Please see the following Google Drive for further details or any missing information: https://drive.google.com/open?id=1WDb18wvwIIfakell7cuK-VCmb6b-gV
	Criteria
			
ICD-10 codes are not listed in this document because of excel file size limitations and excessive number of ICD-10 codes. Full ICD-10 code lists will be available in the above Google Drive Folder (link above). ICD-9 to ICD-10 code conversions were completed using a SAS macro that implements forward/ backward mapping based on the CMS ICD-9 to ICD-10 mapping: https://www.ncbi.nlm.nih.gov/pmc/articles/PMC3070730/
	Adequate mapping in claims
		EXPOSURE vs. COMPARISON		
	Rivaroxaban vs. Warfarin	Rivaroxaban 20mg OR 15mg daily (if low GFR) vs. adjusted-dose warfarin		Intermediate mapping in claims
		PRIMARY OUTCOME		Poor mapping or cannot be measured in claims

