Appendix B: Rivaroxaban vs Warfarin

The c-statistics for the propensity score model, pre-matching was 0.861. The post-matching c-statistic was 0.536.

The c-statistics for the propensity score model, pre-matching was 0.85. The post-matching c-statistic was 0.537.

The c-statistics for the propensity score model, pre-matching was 0.839. The post-matching c-statistic was 0.524.

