...mean (sd)	0.04 (0.28)	0.04 (0.24)	0.00	0.03 (0.25)	0.03 (0.23)	0.00	0.08 (0.37)	0.07 (0.33)	0.03	0.06 (0.33)	0.06 (0.30)	0.00	
...median [IQR]	0.00 [0.00, 0.00]	0.00 [0.00, 0.00]	0.00	0.00 [0.00, 0.00]	0.00 [0.00, 0.00]	0.00	0.00 [0.00, 0.00]	0.00 [0.00, 0.00]	0.00	0.00 (0.37)	0.00 (0.33)	0.00	
Number of tests for microalbuminuria													
...mean (sd)	0.22 (0.66)	0.22 (0.66)	0.00	0.09 (0.43)	0.09 (0.41)	0.00	0.17 (0.50)	0.16 (0.47)	0.02	0.16 (0.52)	0.16 (0.50)	0.00	
...median [IQR]	0.00 [0.00, 0.00]	0.00 [0.00, 0.00]	0.00	0.00 [0.00, 0.00]	0.00 [0.00, 0.00]	0.00	0.00 [0.00, 0.00]	0.00 [0.00, 0.00]	0.00	0.00 (0.58)	0.00 (0.56)	0.00	
Total N distinct ICD9/ICD10 diagnoses at the 3rd digit level Copy													
...mean (sd)	7.69 (8.86)	7.57 (8.88)	0.01	3.87 (6.60)	3.82 (6.57)	0.01	11.49 (12.00)	11.34 (12.10)	0.01	9.15 (10.51)	9.03 (10.58)	0.01	
...median [IQR]	5.00 [0.00, 12.00]	5.00 [0.00, 11.00]	0.00	0.00 [0.00, 5.00]	0.00 [0.00, 5.00]	0.00	8.00 [0.00, 19.00]	8.00 [0.00, 18.00]	0.00	2.63 (11.28)	2.63 (11.34)	0.00	

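### Index calendar time is in neither the propensity score nor the balance table, although cohort entry spans 6.2 to 8.2 years from rivaroxaban's approval and two ICD code systems

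*Combined protocol and SAP*

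**What the plan says.** Section 5.2.1 starts entry on 4 November 2011 in all three databases and closes it on 31 December of 2017 (Medicare), 2018 (MarketScan) or 2019; the last reads "For Optum: November 4, 2011 -December 31, 2019 (end of data availability".

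The first PS holds only age, sex and the comorbidity index. For the rest, Section 6.2 says: "Remaining covariates are defined only after the study has passed the initial feasibility analysis and the initial power assessment and are listed in Table 1". Section 9 then instructs: "The PS should include the complete list of covariates (excluding laboratory values, which are missing in some patients". Table 1 is in Appendix B, once unmatched and once matched.

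Two further statements bear on time. The footnote to the Section 5.3 flowchart says: "Medicare database includes all patients using a novel oral anticoagulant and a subset of patients using warfarin during 2011-2017". Appendix A says: "ICD-9 to ICD-10 code conversions were completed using a SAS macro that implements forward/ backward mapping".

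Sections 13.1 and 13.2, which would hold the primary and sensitivity analyses, are headings only in this version.

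**The concern.** A newly approved drug is compared with an established one over the new drug's whole uptake period. If rivaroxaban and warfarin starters are spread differently over the years, any change over time in stroke risk, in care or in how events are coded mixes with the drug effect. Appendix A prints the stroke outcome codes as ICD-9 and leaves the ICD-10 equivalents to the mapping, so event capture itself could change within the window.

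Index date is the variable that would show or exclude this, and it is absent. Section 9 and the stop in Section 10 exist so that comparability can be judged before outcomes are seen. With this table nobody can judge it for calendar time. The aim at stake is agreement with the trial's hazard ratio of 0.79, more than the non-inferiority test.

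**Working it through.** **1. Is the variable really absent?** All rows of Appendix B, unmatched and matched, were read for an index date, year, quarter, period or coding era. There is none. No section provides for matching, stratification, adjustment or a sensitivity analysis on calendar time.

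**2. Length of entry, from 4 November 2011 (Section 5.2.1).**
- Medicare: 2,249 days / 365.25 = 6.16 years
- MarketScan: 2,614 / 365.25 = 7.16 years
- Optum: 2,979 / 365.25 = 8.16 years

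**3. Do listed variables stand in for index date?** The two nearest are these (standardised differences in the order Optum, MarketScan, Medicare):

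| Row of Table 1 | Unmatched | Matched |
|---|---|---|
| Distinct diagnosis count | -0.36, -0.26, -0.25 | 0.01, 0.01, 0.01 |
| Days in database before index | -0.07, -0.09, 0.22 | 0.00, 0.02, -0.01 |

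Both are balanced after matching. Neither is index date. Days in database measures look-back, and two patients with equal look-back can start in different years. The row "Total N distinct ICD9/ICD10 diagnoses at the 3rd digit level Copy" has a lower quartile of 0 in every matched arm and a median of 0 in MarketScan, so for those patients it says nothing about when they started.

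**4. Does censoring reveal a time difference?** In the Section 9 table the row "Specified date reached (Dec 17/Dec 18/Dec 19" gives, for the matched cohort:
- rivaroxaban 3,626 / 51,318 = 7.07%
- warfarin 3,196 / 51,318 = 6.23%

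The difference is 0.84 points, a standardised difference of 0.03. Later rivaroxaban entry would produce this, but so would longer persistence. The upper quartile of follow-up is 231 vs 190 days (Optum), 281 vs 192 (MarketScan) and 228 vs 188 (Medicare). It does not settle the question.

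**5. The plan's power, reproduced.** Section 10, pooled: 102,636 matched patients at 10.08 per 1,000 give 1,034.57 events.
- SE(log HR) = sqrt(4 / 1,034.57) = 0.0622
- Superiority at HR 0.79: Φ(0.2357 / 0.0622 − 1.96) = 0.966, as printed
- Non-inferiority at 1.46 with true HR 1: 0.99998, as printed

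**6. Illustration of size.** The documents give no index-year data, so the inputs are assumptions: a gap of 0.5 to 1.5 years in mean index date and a 2 to 5% yearly change in recorded risk.
- Low end: 0.98^0.5 = 0.990 (reciprocal 1.010); |log| = 0.0101, or 0.16 SE
- High end: 0.95^1.5 = 0.926 (reciprocal 1.080); |log| = 0.0769, or 1.24 SE
- Gap needed for a shift of one SE: 0.0622 / 0.0202 = 3.1 years at 2% a year; 0.0622 / 0.0513 = 1.2 years at 5% a year

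If a true HR of 0.79 were attenuated by 1.080 it would become 0.853, and superiority power would be Φ((0.2357 − 0.0769) / 0.0622 − 1.96) ≈ 0.72.

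**7. Room to lose pairs in a re-match.** Events needed for 90% superiority power: 4 × (1.96 + 1.2816)² / (ln 0.79)² = 756, which is 73.1% of 1,034.6. About 26.9% of pairs could go before pooled power falls below 0.90, assuming the same risk per patient.

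**The case against.** The strongest reply is that no imbalance has been shown and that the evidence available points the other way. The matched differences in mean look-back, rivaroxaban minus warfarin, are only +1.8, −22.2 and +6.7 days, so the gap assumed in the illustration is roughly 8 to 25 times the largest of them. If look-back tracked index date one for one, 22 days at 5% a year would be about 0.3%, or 0.05 SE. The diagnosis count was clearly unbalanced before matching and is level afterwards. Opening entry at approval also keeps out pre-approval warfarin starters. Even an adverse shift of 1.24 SE leaves pooled non-inferiority power near 0.998: (0.378 − 0.077) / 0.0622 − 1.96 = 2.89. Finally, the fitted PS is not printed as such. Table 1 carries both component rows and combined rows marked for the PS, so its content is inferred.

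Much of this stands. The bias may be negligible, non-inferiority is not in doubt, and some time-linked difference was probably removed through the proxies. It does not close the gap. Look-back depends on when enrolment began as well as on the index date, so the one-for-one reading is itself an assumption. Balance should not be presumed for an unlisted variable when some listed ones stay apart in matched MarketScan: digoxin 0.13, electrocardiogram −0.11, echocardiogram −0.11. The PS content follows from Section 9's own instruction, and whatever the fitted model held, the balance table shows nothing on index date.

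**Conclusion.** The point holds as a gap in control and in reporting. The plan neither includes index calendar time in the stated PS covariates nor displays it, over entry windows of 6.2 to 8.2 years. Whether the matched arms differ in time, and in which direction that would move the hazard ratio, cannot be learned from the documents. Under the assumed range the effect runs from negligible (0.16 SE) to more than one standard error (1.24 SE) in either direction. Medicare deserves most attention. It supplies 31,068 of 51,318 pairs (60.5%) and about 72% of expected events (748.7 of 1,034.6), and the plan does not say how its warfarin subset is spread over the years. This is a change the plan should make; confidence in its practical importance is medium.

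**What to change.** Add categorical index year to the PS in each database, re-match before any outcome analysis, and add index-year rows to Table 1 by arm and database, before and after matching. Exact matching on year is not required.

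Every patient already has the variable, and it is fixed before treatment. The costs are a re-match in three databases, some lost pairs, and a repeat of the Section 9 and 10 balance, power and sign-off steps, which the investigators and FDA had already reviewed (9/8/20 and 9/29/20). The number of pairs lost is unknown. Pre-match c-statistics are already 0.839 to 0.861, and matching keeps 51,318 of 73,269 rivaroxaban users (70.0%). The 26.9% allowance worked out above is the yardstick for judging that loss.

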5.2.2 Specify inclusion/exclusion criteria for cohort entry and define the index date

Inclusion and exclusion criteria were adapted from the trial as closely as possible. Definitions for all inclusion/exclusion are provided in **Appendix A** and are summarized in the flowcharts below.

5.3 Flowchart of the study cohort assembly

For rivaroxaban vs. warfarin

	Optum		Truven		Medicare	
	Less Excluded Patients	Remaining Patients	Less Excluded Patients	Remaining Patients	Less Excluded Patients	Remaining Patients
All patients		75,894,642		200,203,908		6,886,908
Did not meet cohort entry criteria	-74,960,282	934,360	-199,073,812	1,130,096	-2,028,461	4,858,447
Excluded due to insufficient enrollment	-92,301	842,059	-95,091	1,035,005	-1,551,114	3,307,333

Excluded due to prior use of referent	-482,398	359,661	-622,538	412,467	-2,080,069	1,227,264
Excluded due to prior use of exposure	-205,565	154,096	-204,425	208,042	-660,796	566,468
Excluded because patient qualified in >1 exposure category	-7	154,089	-26	208,016	-81	566,387
Excluded based on Age	-624	153,465	0	208,016	-155	566,232
Excluded based on Gender	0	153,465	0	208,016	0	566,232
Excluded based on Inclusion #1 - Age >=18	-86	153,379	-264	207,752	-65	566,167
Excluded based on Inclusion #2 & 3 - Atrial fibrillation	-83,438	69,941	-129,172	78,580	-348,521	217,646
Excluded based on Inclusion #4	-13,297	56,644	-16,046	62,534	-36,136	181,510
Excluded based on Exclusion #1a - Mitral stenosis	-275	56,369	-154	62,380	-399	181,111
Excluded based on Exclusion #1b - Prosthetic heart valve	-1,238	55,131	-789	61,591	-3,016	178,095
Excluded based on Exclusion #1e - atrial myxoma or left ventricular thrombus	-158	54,973	-35	61,556	-234	177,861
Excluded based on Exclusion #1f - Active infective endocarditis	-279	54,694	-138	61,418	-401	177,460
Excluded based on Exclusion #2a - Active bleeding or bleeding history	-3,413	51,281	-2,716	58,702	-8,256	169,204
Excluded based on Exclusion #2b.1 - Major Surgery	-1,564	49,717	-1,561	57,141	-6,484	162,720
Excluded based on Exclusion #2b.2 - Bleeding diathesis	-1,235	48,482	-885	56,256	-3,832	158,888
Excluded based on Exclusion #2b.3 - Intracranial neoplasm, AV malformation, cerebral aneurysm	-259	48,223	-283	55,973	-422	158,466
Excluded based on Exclusion #2d - Thrombocytopenia	0	48,223	0	55,973	0	158,466
Excluded based on Exclusion #2e - Uncontrolled hypertension	-47	48,176	-105	55,868	-300	158,166
Excluded based on Exclusion #3a.1 - stroke plus disabling stroke effects	-257	47,919	-152	55,716	-847	157,319
Excluded based on Exclusion # 3a.2 - stroke	-103	47,816	-88	55,628	-642	156,677
Excluded based on Exclusion #3b - TIA	-17	47,799	-25	55,603	-123	156,554
Excluded based on Exclusion #3c - DVT & PE	-1,095	46,704	-853	54,750	-3,185	153,369
Excluded based on Exclusion #3d.1 - Use of aspirin > 100 mg, #3d.2 - Use of fibrinolytic agents, #3d.3 - Use of Aspirin + thienopyridines, #3d.4 - Use of cangrelor, #3f - Use of CYP inhibitors, #3g - Use of CYP inducers	-1,020	45,684	-1,024	53,726	-4,503	148,866
Excluded based on Exclusion #3h – Anemia & #3i - Pregnancy	-1,382	44,302	-1,294	52,432	-6,940	141,926
Excluded based on Exclusion #3k - HIV infection	-13	44,289	-7	52,425	-12	141,914

Excluded based on Exclusion #3l - Severe renal impairment	-3,281	41,008	-2,012	50,413	-7,391	134,523
Excluded based on Exclusion #3m - Liver disease	-192	40,816	-170	50,243	-466	134,057
Excluded based on Exclusion #4a - CCI (180 days)- ICD9 and ICD10 v2	-40	40,776	-31	50,212	-400	133,657
Excluded based on Exclusion #4b - drug addiction or alcohol abuse	-157	40,619	-106	50,106	-231	133,426
Excluded based on Exclusion #4f - Non-compliance	-15	40,604	-21	50,085	-196	133,230
Final cohort		40,604		50,085		133,230

Due to CMS cell suppression policy, all values less than 11 are denoted with **

* Medicare database includes all patients using a novel oral anticoagulant and a subset of patients using warfarin during 2011-2017.

6. Variables

6.1 Exposure-related variables:

Study drug:

The study exposure of interest is initiation of rivaroxaban. Initiation will be defined by no use of rivaroxaban or a comparator in the prior 6 months before treatment initiation (washout period).

Comparator agents-

- Initiators of rivaroxaban will be compared to initiators of-
 - Warfarin

6.2 Covariates:

- Age
- Sex
- Combined Comorbidity Index (CCI), measured over the baseline covariate assessment period, defined as 180 days prior to and including index date

Covariates listed above represent only a small subset of covariates that will ultimately be controlled for in the design and analysis. We use the covariates above only for initial feasibility analyses to judge whether there is likely to be sufficient overlap between treatment groups to proceed with the study. Remaining covariates are defined only after the study has passed the initial feasibility analysis and the initial power assessment and are listed in Table 1 (**Appendix B**).

6.3 Outcome variables and study follow-up:

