6.3.2 Study follow-up

Both as-treated (AT) and intention-to-treat (ITT) analyses will be conducted with treatment defined as the index drug on day of cohort entry. Because adherence in the real-world databases is expected to be much worse than in the trial, the AT analysis is the primary analysis, as it targets the relative hazard of outcomes on treatment.

For the as-treated analyses, the follow-up will start the day after initiation of rivaroxaban and comparator and will continue until the earliest date of the following events:

- The first occurrence of the outcome of interest, unless otherwise specified for selected outcomes,
- The date of end of continuous registration in the database,
- End of the study period,
- Measured death event occurs,
- Nursing home admission
 - Nursing home admissions are considered a censoring event because the data sources utilized typically provide little to no data on a patient, particularly on drug utilization, after admission. We will utilize this as an exclusion reason for cohorts for the same reason.

- The date of drug discontinuation, defined as the date of the last continuous treatment episode of the index drug (rivaroxaban and comparator) plus a defined grace period (i.e., 10 days after the end of the last prescription's days' supply in main analyses).
- The date of augmentation or switching from exposure to comparator or vice versa or augmentation/switching to any other NOAC (e.g. switching from rivaroxaban or warfarin to apixaban would be a censoring event);
 - A dosage change on the index treatment does not fulfill this criterion
 - An added treatment that is not part of the exposure or comparator group does not fulfill this criterion

For the intention-to-treat (ITT) analyses, the censoring based on the augmentation/switching and treatment discontinuation will be replaced with a maximum allowed follow-up time of 365 days.

7. Initial Feasibility Analysis

Action report name:

For rivaroxaban vs. warfarin

Optum- <https://bwh-dope.aetion.com/projects/details/1310/results/58054/result/0>

Truven- <https://bwh-dope.aetion.com/projects/details/1313/results/58055/result/0>

Medicare- <https://bwh-dope.aetion.com/projects/details/1341/results/58058/result/0>

Date conducted: 09/02/2020

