Exposed	8,950	Exposed	8,950
Risk per 1,000 patients	7.00	Risk per 1,000 patients	7.00
Desired HR from RCT	0.79	Assumed HR from RCT	1
Alpha (2-sided)	0.05	Alpha (2-sided)	0.05
		Non-inferiority margin	1.46
Number of events expected	125.3	Number of events expected	125.3
Power	0.261393559	Power	0.562809862

o MarketScan

Superiority Analysis		Non-inferiority Analysis	
Number of patients matched	22,600	Number of patients matched	22,600
Reference	11,300	Reference	11,300
Exposed	11,300	Exposed	11,300
Risk per 1,000 patients	7.33	Risk per 1,000 patients	7.33
Desired HR from RCT	0.79	Assumed HR from RCT	1
Alpha (2-sided)	0.05	Alpha (2-sided)	0.05
		Non-inferiority margin	1.46
Number of events expected	165.658	Number of events expected	165.658
Power	0.329138572	Power	0.682759594

- Medicare

Superiority Analysis		Non-inferiority Analysis	
Number of patients matched	62,136	Number of patients matched	62,136
Reference	31,068	Reference	31,068
Exposed	31,068	Exposed	31,068
Risk per 1,000 patients	12.05	Risk per 1,000 patients	12.05
Desired HR from RCT	0.79	Assumed HR from RCT	1
Alpha (2-sided)	0.05	Alpha (2-sided)	0.05
		Non-inferiority margin	1.46
Number of events expected	748.7388	Number of events expected	748.7388
Power	0.897079133	Power	0.999353731

- Stop analyses until balance and final power assessment are reviewed by primary investigators, FDA, and assigned members of advisory board.

Reviewed by PI:	[name]	Date reviewed:	9/8/20
Reviewed by FDA:	[name]	Date reviewed:	9/29/20
Reasons for stopping analysis (if required):			

11. Study Confidence and Concerns

Deadline for voting on study confidence and listing concerns:

Date votes and concerns are summarized:

- If final feasibility and power analyses are reviewed and approved, proceed to the remaining protocol steps.

- All study team and advisory board members that review this protocol should at this stage provide their level of confidence for the success of the RWD study in the [Google Form](#). This form also provides space for reviewers to list any concerns that they feel may contribute to a failure to replicate the findings of the RCT, including differences in study populations, poor measurement of study variables, or residual confounding. All responses will be kept confidential and individual-level results will only be shared with the individual respondent.
- After the deadline for voting has passed, provide the distribution of responses and summarize all concerns here.

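### Unless the Medicare warfarin subset is exhaustive, a warfarin initiator's chance of being in the Medicare cohort depends partly on NOAC use after the index date

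*Combined protocol and SAP*

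**What the plan says.** The make-up of the Medicare file appears only in a footnote to the flowchart in section 5.3: "Medicare database includes all patients using a novel oral anticoagulant and a subset of patients using warfarin during 2011-2017". Section 5.2.1 sets Medicare cohort entry from 4 November 2011 to the end of data on 31 December 2017, so the footnote's years cover the whole entry and follow-up period.

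Section 5.2 forms both arms by one rule: "New users (defined as no use in 180 days prior to index date) of an exposure and a comparator drug will be identified". It does not distinguish warfarin users drawn into the subset from those present because they used a NOAC. Section 6.1 repeats the washout and names only rivaroxaban and the comparator.

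The plan expects NOAC use after a warfarin start. In the primary as-treated analysis of section 6.3.2, "switching from rivaroxaban or warfarin to apixaban would be a censoring event". In the intention-to-treat analysis, "censoring based on the augmentation/switching and treatment discontinuation will be replaced with a maximum allowed follow-up time of 365 days".

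The document gives no sampling rule, fraction or weight for the subset. Section 13.2 (sensitivity analyses) is a heading without content.

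**The concern.** Take two similar patients who start warfarin in 2012. One moves to a NOAC by 2017 and is in the Medicare file with certainty, as a NOAC user. The other stays on warfarin, stops, or dies without a NOAC, and is in the file only if drawn into the subset. A rivaroxaban initiator is always in, through the index drug. Inclusion is therefore selected partly on the future, and in one arm only.

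The propensity score uses baseline covariates and cannot correct selection on a later dispensing. Censoring at the switch ends follow-up but does not change who got into the file.

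The study exists to set its hazard ratio beside the trial's 0.79 (0.66 to 0.96). A bias of unknown sign in the database with most of the events could make agreement or disagreement an artefact, and a larger sample would not reduce it.

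**Working it through.** **1. The plan's own figures.** Section 10 gives Medicare 62,136 matched patients at 12.05 per 1,000, so 62,136 × 0.01205 = 748.74 expected events. The Schoenfeld formula, power = Φ(|ln HR| × √events / 2 − 1.96), gives 0.897 for superiority at 0.79 and 0.9994 for non-inferiority at 1.46. Pooled (1,034.57 events) it gives 0.966 and 0.99998. All match the plan.

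**2. Weight of Medicare.**
- Patients: 62,136 / 102,636 = 60.5%.
- Events: 748.74 / 1,034.57 = 72.4%. The three databases' own figures sum to 1,039.70; on that base the share is 72.0%.

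**3. Inclusion probabilities.** Every NOAC user is in the file, so any warfarin user missing from it had no NOAC use in 2011-2017. Inclusion is 1 with such use and f without it. If 20% of warfarin initiators later use a NOAC (an assumption), their share in the file is 0.20 / (0.20 + 0.80f): 24% at f = 0.8 and 33% at f = 0.5.

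**4. Is f = 1 for eligible patients?** If the subset had been limited to AF patients, few should fail the AF step. In the flowchart, 348,521 / 566,167 = 61.6% fail in Medicare, against 54.4% in Optum (83,438 / 153,379) and 62.2% in Truven (129,172 / 207,752). The counts show no sign of an AF restriction, but they do not exclude one.

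**5. Effect on the warfarin risk.** Let q1 and q0 be the probability of NOAC use by 2017 with and without an outcome event. For a rare event the observed warfarin risk is multiplied by [q1 + (1 − q1)f] / [q0 + (1 − q0)f]. Assume q0 = 0.20 and q1 = 0.10 or 0.30:

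| f | q1 = 0.10 | q1 = 0.30 |
|---|---|---|
| 0.8 | 0.82 / 0.84 = 0.98 | 0.86 / 0.84 = 1.02 |
| 0.5 | 0.55 / 0.60 = 0.92 | 0.65 / 0.60 = 1.08 |
| 0.25 | 0.325 / 0.40 = 0.81 | 0.475 / 0.40 = 1.19 |

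**6. Effect on the pooled hazard ratio.** Weight Medicare by its event share, so the observed HR = 0.79 × factor^(−0.724).
- f = 0.8: 0.78 to 0.80.
- f = 0.5: 0.75 to 0.84. With SE(log HR) = 2 / √1,034.57 = 0.062, this is a shift of about one standard error. In the unfavourable direction, superiority power falls from 0.97 to 0.79.

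**7. Plausible f.** The unmatched warfarin:rivaroxaban ratio is 92,403 / 40,652 = 2.27 in Medicare, 1.73 in Optum (25,701 / 14,869) and 1.82 in MarketScan (32,295 / 17,748). With 20% later NOAC use, the full Medicare ratio would be 2.27 / (0.20 + 0.80f): 2.7 at f = 0.8, 3.8 at f = 0.5 and 5.7 at f = 0.25. Age mix and calendar years differ, so this is indicative only, but 0.25 looks unlikely.

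**8. Dependence on the outcome.** A simulation with true HR 1 assumed yearly rates of 2.5% for stroke, 5% for death, 10% for NOAC uptake and 2.0 for discontinuation. If stroke does not change uptake, the apparent as-treated HR is 1.00 to 1.01, although the one-year warfarin death rate in the file falls to 0.83 of its true value at f = 0.5. If stroke triples uptake, the apparent HR is 0.94 at f = 0.8 and 0.83 at f = 0.5.

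**9. Without Medicare.** Optum 125.30 + MarketScan 165.66 = 290.96 expected events in 40,500 patients. Power is 0.52 for superiority and 0.90 for non-inferiority.

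**The case against.** The strongest reply is that the footnote does not say how the subset was drawn. A subset defined by diagnosis or enrolment could hold every eligible AF initiator, and then nothing is wrong. The AF attrition does not settle this: the AF step needs repeated diagnoses at least 14 days apart within 12 months, so patients coded once or earlier also fail, and NOAC users without AF are in the denominator. The absence of a sampling flag is likewise inferred from silence, since implementation is archived in a platform that is not part of the document. These points stand, and they make the finding conditional.

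The size also rests on assumed inputs. With q1 = 0.18 or 0.22 at f = 0.5, the factor is only 0.98 or 1.02. Even with the wider gap at f = 0.5, a true 0.79 keeps an upper limit of at most 0.95, and a true 1.00 stays non-inferior with an upper limit of at most 1.20.

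Three stronger readings are tempting but unsupported:

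- A reader might infer that later NOAC use decides whether a warfarin initiator can enter at all. Never-NOAC patients in the subset do enter; only the probability changes.
- A reader might infer that event-free time before a switch must lower the warfarin stroke rate. Median Medicare warfarin follow-up is 98 days, and step 8 shows almost no effect on the as-treated HR unless uptake depends on the outcome. A switch after a bleed that is not a stroke adds no primary event.
- A reader might infer that restricting to the subset is always safe. If the subset was drawn only from never-NOAC users, restriction would leave only never-switchers and make the selection worse.

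**Conclusion.** The concern holds conditionally. On the footnote's plain reading, taking all warfarin initiators from the Medicare file selects partly on the future in one arm, unless the subset is complete for eligible patients. Nothing in the document says it is, and the attrition counts do not suggest it.

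Neither size nor direction can be determined, because f, the sampling rule and the link between outcome and NOAC uptake are not given. The section 9 censoring table cannot help: it is pooled and merges NOAC switching with nursing home admission (13.84% warfarin, 12.42% rivaroxaban). Under the stated assumptions the effect is negligible at f = 0.8 and about one standard error of the pooled log hazard ratio at f = 0.5. Larger biases need an f that the ratio of 2.27 makes unlikely, or a stronger link between stroke and uptake than the 10%-to-30% range assumed. Because Medicare carries most of the events, this should be settled before the comparative analysis.

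**What to change.** Before outcomes are opened, establish how the warfarin subset was drawn and record the rule and f in section 5.3. Then:

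- **(a) Drawn regardless of NOAC use, with a flag:** take Medicare warfarin initiators only from the subset.
- **(b) Drawn only from never-NOAC users, or no flag:** do not restrict. Keep all warfarin initiators and weight those with no NOAC dispensing in 2011-2017 by 1/f, in both the propensity model and the outcome analysis.
- **(c) All eligible warfarin initiators included:** say so in the footnote and change nothing.
- **(d) Neither rule nor f recoverable:** report the Optum plus MarketScan estimate beside the pooled one, and state that the Medicare warfarin arm may be selected on later NOAC use. With about 291 expected events, that estimate has power of about 0.52 for superiority and 0.90 for non-inferiority, so it is a check rather than a replacement.

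Options (a) and (b) cost a Medicare re-match, a re-run of the affected parts of sections 7 to 10, and renewed review at stop points that the investigator and the regulator have already signed off. Option (a) loses some Medicare warfarin patients; option (b) loses some precision. Options (c) and (d) need no rebuild. The comparative-analysis date in section 13 is blank, so on the document's face there is still time.
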